7.2.2 SAE reporting

To ensure patient safety, every SAE, regardless of causality, occurring after the patient has provided informed consent and until 30 days after the patient has stopped study participation (defined as time of last dose of study drug taken or last visit whichever is later) must be reported to Novartis within 24 hours of the investigator learning of its occurrence / receiving follow up information. Any SAEs experienced after the 30 day period after the last study visit should only be reported to Novartis if the investigator suspects a causal relationship to study treatment.

Recurrent episodes, complications, or progression of the initial SAE must be reported as followup to the original episode, regardless of when the event occurs. This report must be submitted within 24 hours of the investigator receiving the follow-up information. An SAE that is considered completely unrelated to a previously reported one should be reported separately as a new event

Information about all SAEs is collected and recorded on the Serious Adverse Event Report Form; all applicable sections of the form must be completed in order to provide a clinically thorough report. The investigator must assess the relationship of each SAE to each specific component of study treatment, (if study treatment consists of several components) complete the SAE Report Form in English, and submit the completed form within 24 hours to Novartis. Detailed instructions regarding the submission process and requirements for signature are to be found in the investigator folder provided to each site.

Page 65

Follow-up information is submitted as instructed in the investigator folder. Each re-occurrence, complication, or progression of the original event must be reported as a follow-up to that event regardless of when it occurs. The follow-up information should describe whether the event has resolved or continues, if and how it was treated, whether the blind was broken or not, and whether the patient continued or withdrew from study participation.

If the SAE is not previously documented in the Investigator's Brochure or Package Insert (new occurrence) and is thought to be related to the study drug a Drug Safety and Epidemiology Department associate may urgently require further information from the investigator for Health Authority reporting. Novartis may need to issue an Investigator Notification (IN) to inform all investigators involved in any study with the same study drug that this SAE has been reported. Suspected Unexpected Serious Adverse Reactions (SUSARs) will be collected and reported to the competent authorities and relevant ethics committees in accordance with European Union (EU) Guidance 2011/C 172/01 or as per national regulatory requirements in participating countries.

7.2.3 Pneumonia reporting

Pneumonia will be defined as an event characterized by increased respiratory symptoms (e.g. increased cough, dyspnea, wheezing, purulent sputum), fever (i.e., body temperature greater than 38°C) or pleuritic chest pain or leukocytosis or other clinical signs consistent with pneumonia considered relevant in the opinion of the investigator and confirmed by X-ray. Any reported pneumonia will have to be confirmed a by radiologist's interpretation of a chest X-ray (to be kept in the source documents). If not confirmed by X-ray, it should be reported as lower respiratory tract infection.

7.3 Liver safety monitoring

To ensure patient safety and enhance reliability in determining the hepatotoxic potential of an investigational drug, a standardized process for identification, monitoring and evaluation of liver events has to be followed.

The following two categories of abnormalities/AEs have to be considered during the course of the study (irrespective of whether classified/reported as (S)AE):

- Liver laboratory triggers, which will require repeated assessments of the abnormal laboratory parameter
- Liver events, which will require close observation, follow-up monitoring and completion of the standard base liver eCRF pages

Please refer to Table 8-1 in Appendix 8 for complete definitions of liver laboratory triggers and liver events.

Every liver laboratory trigger or liver event as defined in Table 8-1 in Appendix 8 should be followed up by the investigator or designated personal at the trial site as summarized below. Detailed information is outlined in Table 8-2 in Appendix 8.

For the liver laboratory trigger:

Repeating the liver function test (LFT) within the next week to confirm elevation.

These LFT repeats should be performed using the central laboratory if possible. If this is not possible, then the repeats can be performed at a local laboratory to monitor the safety of the patient. Repeats laboratory should then be performed at central laboratory as soon as possible. If a liver event is subsequently reported, any local LFTs previously conducted that are associated with this event should be reported on the Liver eCRF pages.

If the elevation is confirmed, close observation of the patient will be initiated, including consideration of treatment interruption if deemed appropriate.

For the liver events:

- Repeating the LFT to confirm elevation as appropriate
- Discontinuation of the investigational drug if appropriate
- Hospitalization of the patient if appropriate
- A causality assessment of the liver event via exclusion of alternative causes (e.g., disease, co-medications)
- An investigation of the liver event which needs to be followed until resolution.

These investigations can include serology tests, imaging and pathology assessments, hepatologist's consultancy, based on investigator's discretion. All follow-up information, and the procedures performed should be recorded on appropriate eCRF pages, including the liver event overview eCRF pages.

7.4 **Pregnancy reporting**

To ensure patient safety, each pregnancy occurring after signing of the informed consent must be reported to Novartis within 24 hours of learning of its occurrence. The pregnancy should be followed up to 3 months following the birth of your child to determine outcome, including spontaneous or voluntary termination, details of the birth, and the presence or absence of any birth defects, congenital abnormalities, or maternal and/or newborn complications. Pregnancy follow up period can be increased if requested by health authorities.

Pregnancy should be recorded on the Pharmacovigilance Pregnancy Form and reported by the investigator to the local Novartis Drug Safety and Epidemiology Department. Pregnancy follow-up should be recorded on the same form and should include an assessment of the possible relationship to the investigational/study treatment.

Any SAE experienced during the pregnancy and unrelated to the pregnancy must be reported on a SAE form.

8 Data review and database management

8.1 Site monitoring

Before study initiation, at a site initiation visit or at an investigator's meeting, a Novartis representative will review the protocol and eCRFs with the investigators and their staff. During the study, Novartis employs several methods of ensuring protocol and Good Clinical Practice (GCP) compliance and the quality/integrity of the sites' data. The field monitor will visit the site to check the completeness of patient records, the accuracy of entries on the eCRFs, the adherence to the protocol and to Good Clinical Practice, the progress of enrollment, and to ensure that study treatment is being stored, dispensed, and accounted for according to specifications. Key study personnel must be available to assist the field monitor during these visits. Continuous remote monitoring of each site's data may be performed by a centralized Novartis Clinical Research Associate (CRA) organization. Additionally, a central analytics organization may analyze data and identify risks and trends for site operational parameters, and provide reports to Novartis Clinical Teams to assist with trial oversight.

The investigator must maintain source documents for each patient in the study, consisting of case and visit notes (hospital or clinic medical records) containing demographic and medical information, laboratory data, ECGs, and the results of any other tests or assessments. All information on eCRFs must be traceable to these source documents in the patient's file. The investigator must also keep the original informed consent form signed by the patient (a signed copy is given to the patient).

The investigator must give the monitor access to all relevant source documents to confirm their consistency with the eCRF entries. Novartis monitoring standards require full verification for the presence of informed consent, adherence to the inclusion/exclusion criteria, documentation of SAEs, and of data that will be used for all primary variables. Additional checks of the consistency of the source data with the eCRFs are performed according to the study-specific monitoring plan. No information in source documents about the identity of the patients will be disclosed.

8.2 Data collection

Designated investigator staff will enter the data required by the protocol into the (OC/RDC) system. Designated investigator site staff will not be given access to the system until they have been trained.

Automatic validation procedures within the system check for data discrepancies during and after data entry and, by generating appropriate error messages, allow the data to be confirmed or corrected online by the designated investigator site staff. The Investigator must certify that the data entered into the eCRFs are complete and accurate. After database lock, the investigator will receive copies of the patient data for archiving at the investigational site.

8.3 Database management and quality control

Novartis staff (or a designated Contract Research Organization (CRO)) staff will review the data entered into the eCRFs by investigational staff for completeness and accuracy and instruct the site personnel to make any required corrections or additions. Queries are sent to the

investigational site using an electronic data query. Designated investigator site staff is required to respond to the guery and confirm or correct the data.

Page 68

Concomitant medications entered into the database will be coded using the WHO Drug Reference List, which employs the Anatomical Therapeutic Chemical classification (ATC) system. Concomitant procedures, non-drug therapies and AEs will be coded using the Medical dictionary for regulatory activities (MedDRA) terminology.

Laboratory samples will be processed centrally and the results will be sent electronically to Novartis (or a designated CRO).

ECG readings will be processed centrally and the results will be sent electronically to Novartis (or a designated CRO).

Spirometry readings will be processed centrally and the results will be sent electronically to **Novartis**

Diary data will be entered into an electronic diary by the patient. The system will be supplied by a vendor(s), who will also manage the database. The database will be sent electronically to Novartis.

Randomization codes and data about all study drug(s) dispensed to the patient and all dosage changes will be tracked using an Interactive Response Technology (IRT). The system will be supplied by a vendor, who will also manage the database. The database will be sent electronically to Novartis (or a designated CRO).

Each occurrence of a code break via IRT will be reported to the clinical team and monitor. The code break functionality will remain available until study shut down or upon request of Novartis.

The occurrence of relevant protocol deviations will be determined. After these actions have been completed and the database has been declared to be complete and accurate it will be locked and the treatment codes will be unblinded and made available for data analysis. Any changes to the database after that time can only be made after written agreement by Novartis Development management.

8.4 **Data Monitoring Committee**

An independent, external data safety monitoring committee (DMC) will be set up to review all SAEs (including deaths and all hospitalizations). DMC members will review this data generated externally and independently of Novartis, at predetermined intervals. If significant safety issues arise in between scheduled meetings, ad-hoc meetings will be scheduled to review the data. Based on the safety implications of the data, the DMC may need to recommend modification or termination of the study.

The details of the information flow, confidentiality and specific analyses required for the safety monitoring analysis will be documented in a DMC Charter.

The DMC is the autonomous data and safety advisory group for Novartis. The DMC charter will be developed as a separate document. The charter will define:

- 1. Membership of DMC
- 2. Responsibilities of DMC and Novartis

- 3. Responsibilities of independent biostatistician and programmer
- 4. The relationship of DMC with other trial components and data flow
- 5. The purpose and timing of DMC meetings
- 6. Procedures for ensuring proper confidentiality, addressing conflict of interest, and ensuring proper communication

The charter complies with Novartis SOPs and is in accordance with the FDA guidance and CHMP guidelines on DMCs.

8.5 **Adjudication Committee**

An independent external adjudication committee will be established to assess serious asthma outcomes (asthma-related hospitalizations, intubations and deaths). All serious asthma outcomes, and deaths occurring from the time of randomization until the 30 days after the permanent discontinuation of study drug, where applicable, will be adjudicated.

The committee will consist of experts outside Novartis who are not involved in the study conduct, who will periodically review blinded, pertinent patient data and the supporting documentation to settle the specified adjudication objectives.

Further details will be provided in the Adjudication Committee Charter.

8.6 **Advisory Board**

An Advisory Board will be established. This board will consist of a group of independent nonsponsor clinical experts and clinical/medical/statistical sponsor representatives.

In general, the functions of the advisory board may include:

- Data interpretation
- **Publications**
- Presentations

9 Data analysis

The analysis will be conducted on all patient data at the time the trial ends. Measurements made after patients discontinue randomized treatment (off-treatment measures) will not be used for any efficacy evaluation.

Any data analysis carried out independently by the investigator should be submitted to Novartis before publication or presentation.

9.1 **Analysis sets**

The following analysis sets are defined for data analysis.

The randomization (RAN) Set will consist of all patients who were assigned a randomization number, regardless of whether or not they actually received study medication.

The Full Analysis Set (FAS) will consist of all patients in the RAN set who received at least one dose of study medication. Following the intent-to-treat principle, patients will be analyzed according to the treatment they were assigned to at randomization.

The Per-Protocol Set (PPS) will include all patients in the FAS who did not have any major protocol deviations. Major protocol deviations will be defined in the statistical analysis plan prior to database lock and the unblinding of the study. Patients will be analyzed according to the treatment they received.

The Safety Set will consist of all patients who received at least one dose of study medication. Patients will be analyzed according to the treatment they received.

The FAS will be used in the analysis of all efficacy variables. The RAN set will be used for a summary of patient disposition, demographics and baseline characteristics. The PPS will be used for supportive analysis of the primary analysis only. The Safety Set will be used in the analysis of all safety variables.

Note that the FAS and Safety Sets are the same except that the Safety Set allows the inclusion of non-randomized patients who received study drug in error. Also, the FAS assigned randomized treatment and the Safety Set assigned received treatment.

9.2 Patient demographics and other baseline characteristics

Demographic and baseline characteristics measured before randomization including age, gender, race, ethnicity, height, weight, BMI, relevant medical history, Screening spirometry parameters: (FEV₁, FVC, FEV₁/FVC and FEF₂₅₋₇₅), FEV₁ reversibility, percentage of predicted FEV₁, duration of asthma, history of asthma exacerbations, smoking history, prior concurrent medications (asthma-related and non-asthma related), (systolic and diastolic blood pressure, radial pulse rate), QTc using Fridericia's correction and baseline ACQ-7 and AQLQ will be summarized by treatment group.

Continuous variables will be summarized using descriptive statistics (mean, median, standard deviation, minimum, and maximum) and categorical variables will be summarized in terms of the number and percentage of patients in each category.

Baseline is defined as the last measurement before first dose of study drug.

No statistical analyses will be provided for baseline comparability among the treatment groups.

9.3 **Treatments**

Study drug administration and concomitant medication data will be listed and summarized using Safety set.

The duration of exposure and the number of patients randomized who completed the study and who discontinued from study medication will be summarized.

Medications started and stopped prior to study drug, and taken concomitantly will be summarized by treatment group in separate tables in the Safety Set.

Concomitant therapies will be recorded, listed and summarized separately for asthma related medications/non-drug therapies and other medications. Concomitant asthma related medications will be summarized by the route of administration, the recorded pre-specified drug subcategories (including types of combination) and preferred terms. The summary will be repeated by showing ingredients instead of preferred terms. Concomitant medications not related to asthma will be summarized by route of administration and preferred term.

SABA usage (number of puffs) during the Screening epoch will be summarized.

Patients taking prohibited concomitant medications will be noted in the summary of protocol deviations.

Treatment compliance with study medication over the study period will be summarized.

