- QMF149 150/80 microgram o.d. delivered via Concept1
- MF 200 microgram o.d. delivered via Twisthaler®

Randomized patients must have FEV_1 between 60% and < 90% of predicted normal at **both** Visit 101 and Visit 102 and they must qualify for treatment with low dose ICS plus LABA as per GINA 2016 guidelines. At Visit 102, **all** randomized patients must have $ACQ-7 \ge 1.5$. Refer to Section 4.1 Inclusion Criteria for ACQ-7 requirements.

Visit 102 (end of Run-in) and Visit 201(Randomization) must take place sequentially on the same day. The assessments at Visit 102 should be performed prior to administration of the first dose of study medication (Visit 201). Reversibility should NOT be done at Visit 102 (Table 6-1). Randomized patients will enter the 12-week Treatment epoch. All patients will receive both Concept1 and Twisthaler® inhalers (double-blind and double-dummy design). During the treatment epoch, patients will be instructed to inhale study medication once daily in the evening (between 5:00 pm and 8:00 pm).

[figure not shown]
Patients will be followed at regular intervals throughout the 12 week treatment epoch to assess the safety and efficacy of treatment, either by telephone or at clinic visits. Clinic visits are scheduled to take place after 4, and 12 weeks. All clinic visits should occur as scheduled per Table 6-1. Patients will be required to attend the clinic visits to perform trough measurements of lung function (24 hours post dosing) after the first dose of study medication (Visit 201) and after the dose of study medication administered at the clinic after 12 weeks of treatment (Clinic Visit 204). In case of logistical issues, Visit 204 (Week 12) should take place within a 4 day window. If this is not possible, the sponsor should be notified.

Pre-dose FEV_1 measurements will be assessed at Week 4. Telephone reviews of patients' status will be conducted after 8 weeks of treatment. Telephone contact with patients may indicate that a clinic visit is necessary, in which case an unscheduled clinic visit should be arranged as soon as possible and should include safety assessment (AEs, concomitant medications review and unscheduled laboratory exams as appropriate).

A final telephone contact must be conducted at 30-days after last treatment date (telephone Visit 301 or unscheduled visit safety call for patients who discontinue treatment earlier than 12 weeks).

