Visits 102 and 201 should take place sequentially on the same day and Visit 102 assessments should be performed prior to administration of the first dose of study medication (Visit 201).

The scheduled assessments should be performed in the following order: Patient reported outcomes (PROs) (i.e., ACQ, AQLQ), ECG, radial pulse rate, blood pressure and blood /urine samples followed by spirometry (as per Table 6-2).

The details of spirometry assessments are indicated in Table 6-2. An approximate 3 min rest from start of ECG to the start of spirometry manoeuvres should be given. When an ECG is needed to be taken after spirometry, a 10 minute rest from the end of spirometry to start of ECG assessments should be considered.

If other assessments are scheduled at the same time-point, spirometry will take precedence (with the exception of PROs and blood tests) so that it occurs at/or as close as possible to the scheduled time points.

Table 6-1 Assessment schedule

Assessment schedule										
Visit Number	1	101	102	201	202	203 5	20410	Early treatme nt disconti nuation (TD)	Premat ure study discont inuatio n (PSD)	301 ⁹
Epoch	Screen	Run-	in	Trea	tment				PSD	Follow -up
Clinic (C) /Telephone (T)	С	С	С	С	С	Т	С	С	Т	Т
Week – Start of Week	-5 to -3	-3	0	0	4	8	12			16
Day Number	-35 to - 21	-21	1	1/2	30	57	84/856			114
Obtain Informed Consent and/or assent (including for sub-group)	X ¹¹									
Current medication review/ adjustment	X									
Inclusion/exclusion criteria	X	Х	Х							
Randomizatio n via IRT				S						
Medical History, Demography	X									
History of Asthma exacerbation	X									
Smoking history and status	Х									
Run-in medication		Х								
Pregnancy test (serum) ¹		Х			Х		Х	Х		
Pregnancy test (urine) ¹	X		X							

Visit Number	1	101	102	201	202	203	20410	Early treatme nt disconti nuation (TD)	Premat ure study discont inuatio n (PSD)	301 ⁹
Epoch	Screen	Run	-in	Trea	tment				PSD	Follow -up
Clinic (C) /Telephone (T)	С	С	С	С	С	T	С	С	Т	T
Week – Start of Week	-5 to -3	-3	0	0	4	8	12			16
Day Number	-35 to - 21	-21	1	1/2	30	57	84/856			114
Urine analysis (dipstick)		S		S			S	S		
Device training ⁴	S	S	S							
Concomitant medication review	Х	Х	Х	Х	Х	Х	Х	Х	Х	Х
Physical examination		S					S	S		
Oropharyngea I examination		S	S	S	S		S	S		
Record height (for adult patients only at Visit 101) and weight		Х					X ¹²	X ¹²		
ECG ²		Χ		Χ			X	X		
Vital signs ²		Х	Х	Х	Х		Χ	X		
Issue rescue medication as necessary	S	S		S	S					

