6.5.2 Vital signs

Systolic and diastolic blood pressure and radial pulse rate (over a 30 second interval), performed in the sitting position, will be recorded at each scheduled clinic visits as detailed in Table 6-2. (at Visits 101, 102, 201, 202, 204 or TD Visit, if applicable). Vital sign should be measured directly after the ECG assessments.

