### 2.1.1.2 Baseline definition

In general, baseline is defined as the last measurement before the first dose of study treatment at the evening of Day 1.

Parameter	Baseline assessment	Detail
Post-dose FEV 1 , Pre-dose trough FEV 1 , Trough FEV 1	45 min and 15 min pre-dose FEV 1 at Day 1	The average of the values taken at -45 and -15 min
Post-dose FVC, Pre-dose trough FVC, Trough FVC	45 min and 15 min pre-dose FVC at Day 1	The average of the values taken at -45 and -15 min
Post-dose FEF 25-75 , Pre-dose trough FEF 25-75 , Trough FEF 25-75	45 min and 15 min pre-dose FEF 25-75 at Day 1	The average of the values taken at -45 and -15 min
ACQ-7	Prior to first dose of study treatment at Day 1	The average of responses of 7 questions
ACQ-5	Prior to first dose of study treatment at Day 1	The average of responses of first 5 questions
Diary data (PEF, symptoms, and rescue medication use)	Last 21 days of run-in period between run-in Visit 101 and up to one day before first dose of study treatment	The average from all non- missing records or percentage of days free of symptoms or rescue medication use
Laboratory data (hematology, biochemistry, urinalysis, and plasma cortisol)	20 min pre-dose at Day 1	
Vital signs (pulse rate and systolic and diastolic blood pressures)	25 min pre-dose at Day 1	
Height and weight	Run-in Visit 101	
ECG	35 min pre-dose at Day 1	

Detail descriptions for calculating baseline values are provided in the latter sections.

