### **2.8.5.2 Vital signs**

Vital signs measurements include systolic and diastolic blood pressure (SBP and DBP), pulse rate, height (for adolescents only) and body weight (at selected visits only).

Baseline vital signs (systolic and diastolic blood pressure (SBP and DBP), pulse rate) are defined as the assessment taken 25 minutes pre-dose at Day 1. Checks will be performed to ensure the assessments were indeed taken prior to the first dose of study treatment on Day 1. If this assessment is missing or not confirmed to be pre-dose, the last value taken at the run-in Visit 101 or at an unscheduled visit before the first administration of study treatment will be used for baseline. Baseline height and weight are defined as the measurements taken at the run-in Visit 101. Missing baseline values will not be imputed.

Vital signs data measured more than 7 days after last inhalation of study treatment are regarded as post-treatment data and will not be summarized, only listed. All data will be included in the analyses regardless of rescue medication use.

The following analyses will be performed by treatment:

- absolute values and change from baseline summarized by parameter, visit and time point
- the number and percentage of patients by parameter, visit and time point with
  - pulse rate < 40 bpm, 40 – 90 bpm, and > 90 bpm
  - SBP < 90 mm Hg, 90 – 140 mm Hg, and > 140 mm Hg
  - DBP < 50 mm Hg, 50 – 90 mm Hg, and > 90 mm Hg
- the number and percentage of patients with newly occurring or worsening notable vital signs values (see [Section 6.5](#) for definition of notable values) summarized by parameter (except height), scheduled post-baseline visit and time point and additionally at any time on treatment considering all post-baseline data from scheduled, unscheduled and premature discontinuation visits

The by-visit/time point summaries will include the maximum and minimum post-baseline SBP, DBP, and pulse rate values (even if from post-baseline unscheduled and premature discontinuation visits, if not measured more than 7 days after last dose).

The same approach as for notable laboratory values will be used to define a newly occurring notable vital sign value and a worsening notable vital sign value.

[figure not shown]
A listing of all patients with notable vital sign values and changes will be provided.

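### The SAP's fallback baseline for vital signs omits Visit 102, so a patient without a valid Day 1 -25 min reading can get a value about 21 days old

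*Protocol*

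**What the plan says.** **Definition of baseline.** Protocol 9.2 states: "Baseline is defined as the last measurement before first dose of study drug". SAP 2.1.1.2 agrees: "In general, baseline is defined as the last measurement before the first dose of study treatment at the evening of Day 1". It then tabulates parameter-specific baselines.

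**Vital signs in the SAP.** SAP 2.8.5.2 says that baseline blood pressure and pulse "are defined as the assessment taken 25 minutes pre-dose at Day 1". If that assessment is missing or cannot be confirmed as pre-dose, "the last value taken at the run-in Visit 101 or at an unscheduled visit before the first administration of study treatment will be used" instead.

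**Schedule.** Protocol 6.5.2 has vital signs recorded "at Visits 101, 102, 201, 202, 204 or TD Visit, if applicable". Table 6-1 marks Visit 102 with an X for vital signs, its code for data that go into the clinical database. Protocol 3.1 requires that "Visit 102 (end of Run-in) and Visit 201(Randomization) must take place sequentially on the same day", with the Visit 102 assessments done before the first dose.

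**Reporting label.** Table 6-2 footnote 7, attached to Visit 201 Day 1, says that assessments made before randomization are reported under Visit 101.

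**Declared changes.** SAP section 1 says the data will be analyzed according to protocol Section 9. The only change listed in SAP section 4 is the addition of ACQ-5 analyses.

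**The concern.** If the -25 min reading fails, the last measurement before the first dose is normally the Visit 102 reading taken earlier that day. The SAP's list skips it and goes back to the start of run-in, unless an unscheduled visit happens to supply something later.

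The baseline value feeds three outputs for these patients: change from baseline; the notable-change criteria in SAP 6.5 that depend on baseline (for example, pulse of at least 120 bpm with a rise of at least 15 bpm); and whether a notable value counts as newly occurring or worsening. With a beta-2 agonist in one arm only, pulse and blood pressure are summaries that readers will look at. There is no evident reason to measure their change from a three-week-old value when a same-day one was recorded.

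**Working it through.** There is no figure in the plan to reproduce. The check is a comparison of texts, followed by a rough sizing.

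**1. Age of each candidate baseline.** SAP 2.1.1.1 computes study days before first dose as assessment date minus first-dose date. Visit 101 is Day -21 in Table 6-1, so it falls 21 days before dosing. Visit 102 is on Day 1, so it falls 0 days before.

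**2. Which run-in visits supply each parameter, and which ones the fallback names.**

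| Parameter | Pre-dose visits with a databased assessment (Table 6-1) | Visits named in the SAP fallback |
|---|---|---|
| FEV1 | 101, 102, 201 | 101, 102, unscheduled (SAP 2.5.1) |
| Laboratory | 101, 201 | 101, unscheduled (SAP 2.8.4) |
| ECG | 101, 201 | 101, unscheduled (SAP 2.8.5.1) |
| Vital signs | 101, **102**, 201 | 101, unscheduled (SAP 2.8.5.2) |

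For laboratory data and ECG, leaving out Visit 102 costs nothing, because neither is taken there. For FEV1, which is taken there, the SAP names it. Vital signs are the one row where the fallback does not match the schedule. The wording is nearly the same as in the laboratory and ECG sections, so a carry-over is the likely explanation.

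**3. Number of patients.** The documents give no rate of missing or unconfirmed -25 min readings. Assuming 1% to 5% of the planned 750:

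- 750 × 0.01 = 7.5, about 8 patients
- 750 × 0.05 = 37.5, about 38 patients

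**4. Effect on the spread of change from baseline.** Assume equal variance σ² at each time, no mean shift between the two candidate baselines, and a correlation r between baseline and post-dose reading. Then Var(change) = 2σ²(1 − r). The correlations below are assumptions, not taken from the documents.

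- Same-day baseline, r = 0.7: 2(1 − 0.7) = 0.60
- Three-week-old baseline, r = 0.5: 2(1 − 0.5) = 1.00
- SD ratio within affected patients: √(1.00/0.60) = 1.29

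Over the whole sample, with a fraction p affected, the variance is 0.60(1 − p) + 1.00p:

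- p = 0.01: 0.604, so √(0.604/0.600) = 1.003, a rise of about 0.3%
- p = 0.05: 0.620, so √(0.620/0.600) = 1.017, a rise of about 1.7%

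If the two correlations were equal, the ratio would be 1.0 and the spread would not change at all.

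**The case against.** **Footnote 7 may cover it.** Read literally, Table 6-2 footnote 7 could place same-day pre-randomization readings under the Visit 101 label, and the SAP's last Visit 101 value would then pick them up. This is a fair point and not a conclusive one. Table 6-1 gives Visit 102 its own databased vital signs, and SAP 2.5.1 treats Visits 101 and 102 as separate sources. The footnote adds an ambiguity that needs resolving.

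**A separate Visit 102 reading may not exist.** Protocol 6.5.2 refers to Table 6-2 for detail, and that table has no Visit 102 row; its only pre-dose vital-signs slot on Day 1 is -25 min. At a combined visit, one measurement might serve both. The documents do not say so, and Table 6-1 marks the two separately. The point therefore has to be conditional on a Visit 102 reading being present.

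**The fallback will rarely be used.** SAP 2.8 assigns values with missing date or time to their scheduled slot, so a missing timestamp need not trigger it. This stands, and is a reason to expect few affected patients.

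**Nothing inferential depends on it.** This also stands. Vital signs are summarized without a test or model, the rule is the same in both arms, and the absolute categories in SAP 2.8.5.2 do not use baseline.

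**Stronger readings to avoid.** A reader might infer that Visit 101 vital signs are disturbed by the salbutamol given for reversibility testing. Protocol section 6 puts pulse and blood pressure before spirometry, so the scheduled readings come before the bronchodilator. A reader might also take the 1.29 ratio as the effect on the safety tables, but it applies only within the affected patients and rests on assumed correlations. Nor do the documents show any bias between arms.

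**Conclusion.** The SAP's vital-signs fallback departs from the last-measurement rule in protocol 9.2 and SAP 2.1.1.2, and does so without declaration. The departure is confined to patients with no valid -25 min reading who have a Visit 102 reading and no later unscheduled one. For everyone with a valid -25 min reading, the two documents agree.

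The consequence is minor: a less precise baseline for a handful of patients in descriptive safety tables. The primary and key secondary analyses and the sample size are unaffected. The sizing depends on the assumed 1-5% and the assumed correlations; the textual mismatch depends on neither. The remaining uncertainty is how footnote 7 was applied in the database. It is worth correcting because the correction is nearly free.

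**What to change.** In SAP 2.8.5.2, follow the pattern of SAP 2.5.1. Suggested wording: *If this reading is missing or not confirmed as pre-dose, baseline will be the most recent vital signs recorded before the first dose, whether at run-in Visit 101, run-in Visit 102 or an unscheduled visit.* The laboratory and ECG fallbacks can stay as they are.

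Also reconcile Table 6-2 footnote 7 with the separate Visit 102 column in Table 6-1, so that the programmer knows under which visit label the same-day pre-randomization readings are stored. If Visit 102 was left out on purpose, state that and the reason in SAP section 4.

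The cost is a sentence in the SAP and a line of derivation code. If the Visit 102 and -25 min readings prove to be the same measurement, the change has no effect and does no harm.
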